## **1.0 Research Introduction**

### **1.1 Purpose/Specific Aims**

To explore the effects of Transcutaneous Electrical Nerve Stimulation (TENS) therapy in the pain management of postpartum women.

#### **A. Objectives**

- To determine if the addition of TENS therapy to the pain management of women post-C-Section leads to less opioid medication use.
- To evaluate the efficacy of TENS therapy as a means of alternative pain relief for women post-C-section (CS) and for postpartum women with a history of opioid use.

#### **B. Hypotheses / Research Question(s)**

Version Number: 5

Protocol Number: Pro2018001008

PI Name: [name]

Protocol Title: TENS after Cesarean Delivery

3

RESERVED FOR IRB STAMP

DO NOT MODIFY THIS SPACE

IRB ID: Pro2018001008

IRB Form Version 01/2018 Approval Date: 7/19/2022

Expiration Date: 7/18/2023

We hypothesize that patients that receive TENS therapy will report lower pain scores and request less opioid medication than the control group. We anticipate improved control in particular in the group of women with a history of opioid use.

Additionally, we believe that the TENS therapy will show benefits in other postpartum outcomes including time to bowel movement, level of sedation, and time to out of bed.

Overall, we anticipate that this pilot study will support the application of TENS therapy in postpartum pain management.

### **1.2 Research Significance (*Briefly describe the following in 500 words or less*):**

This pilot project will evaluate the effects of Transcutaneous Electrical Nerve Stimulation (TENS) on intensity of incisional symptoms, pain medication usage and patient satisfaction with pain control in women after Cesarean Section (CS).

Over 1 million women in the United States deliver via Cesarean Section (CS) annually. Women are prescribed opioid medications for pain management both during the inpatient stay and upon discharge home following Cesarean Section delivery in the United States (Osmundson et al, 2017; Bateman et al, 2017; Fahey, 2017). Health care providers must balance the risks and benefits of providing opioid pain medications to women after childbirth (Dowell et al, 2016). Alternative pain relief therapies delivered to women in acute post-operative pain after CS during the inpatient hospital stay are critically needed to reduce the quantity of opioids provided to new mothers after birth.

The use of opioid medications for new mothers presents notable risk of adverse events for both mother and baby. Following an incident in which a newborn died from morphine poisoning when his mother was prescribed codeine while breastfeeding, additional research efforts have illuminated the hazards of opioid use in new mothers. Breastfeeding mothers who are rapid metabolizers of CYP450 produce much more morphine from ingested codeine. (FDA.gov) Therefore, there is a risk of infant toxicity when breastfeeding mothers are taking certain opioids. Willman et al (2009) found that “opioids can accumulate in babies despite only small quantities of maternal opioids excreted in breast milk because neonates and babies less than 6 months have as much as a fourfold reduced ability to clear the small quantities of opioids consumed compared to babies older than 6 months.” Elevated levels in newborns can lead to analgesia, sedation, and life-threatening respiratory depression.

In addition to toxicity, prescribing opioids to new mothers, whether breastfeeding or not, bears a risk of misuse and addiction. The Substance Abuse and Mental Health Services Administration reports an annual average of approximately 21,000 pregnant women who have misused opioids in the past month. Access and adherence to opioid use disorder treatment remains a significant hurdle for new mothers. The accumulation of these risks underscore the clinical significance of finding alternative pain relief methods.

Non-pharmacological interventions for pain management, such as Transcutaneous Electrical Nerve Stimulation (TENS), have been shown to reduce painful incisional symptoms and reduce intake of opioid pain medications in women after CS (Jaafarpour et al, 2008; Kerai et al, 2011; Karakaya et al, 2011). TENS is a low-cost, effective intervention that can be applied safely by physical therapists, nurses and physicians on the inpatient floor. Studies have demonstrated that patients can be educated on self-administration of TENS. This pilot project proposes the use of TENS on the inpatient postpartum floor starting at 8 hours post-operatively and continuing until discharge home. It is hypothesized that women who utilize TENS after CS will consume less opioid medication during the inpatient stay compared to women who do not utilize TENS after CS.

### **1.3 Research Design and Methods**

**OVERVIEW.** This study is a pilot randomized interventional trial. Two categories of participants will be randomly assigned to an invention or control group, using a random number generator: normal cesarean without associated comorbidity, or cesarean in women with a history of opioid addiction, as defined by use of opioid replacement medications of either methadone or Subutex during pregnancy. The control group will receive usual care which is

Version Number: 5

Protocol Number: Pro2018001008

PI Name: [name]

Protocol Title: TENS after Cesarean Delivery

4

RESERVED FOR IRB STAMP

DO NOT MODIFY THIS SPACE

IRB ID: Pro2018001008

[figure not shown]
IRB Form Version: 01/2018 Approval Date: 7/19/2022

Expiration Date: 7/18/2023

standard post-operative pain management with opioids and NSAIDS. The intervention group will receive usual care plus TENS therapy beginning 8 hours after C-section and continuing to discharge. Both groups will receive medications for pain as requested or ordered by the doctor.

**RESEARCH PROCEDURES.** Patients will be identified for participation in several locations. Prenatal patients at the Rutgers Medical Group Obstetrics and Gynecology or Maternal Fetal Medicine practices, or the High Risk Obstetric Perinatal Clinic will be approached for study inclusion. Physicians that have a direct treatment relationship with the patient will inform the patient about the study and invite them to enroll. Consent for participation will be reviewed with the principal investigator and signed prior to delivery hospitalization. Randomization will follow consent, and patients randomized to intervention will have teaching performed about how to use the device at the time of consent.

Following cesarean delivery, subjects will be re-approached in the Postpartum Unit at Robert Wood Johnson University Hospital by study staff. The TENS device will be again reviewed, and provided to the patient, with review of instructions for use. The patients in the intervention group will be educated on the proper way to utilize the TENS unit. They will apply the patches of the TENS unit above and below the C-section site. Specifically, the electrode patches will be placed above the abdominal bandages post-operatively and replaced above the abdominal bandages after the dressing change on post-operative day 1. Starting 8 hours after C-Section, the TENS unit will be turned on to a comfortable intensity as determined by the patient and will remain on until the patient is discharged, to be removed for toileting and showering and at the patient's discretion. Once the TENS unit is applied and turned on, the patient will not have to do anything else to maintain the therapy. Study staff will provide a record for documentation of time on/off for the unit. Additionally, a member of the study staff will check on the device daily to ensure proper maintenance. On the day of discharge, study staff will collect the device, and conduct a short survey about pain scores. They will then review pain scores, pain medication usage and other secondary outcomes in the patient's chart. Finally, pain will be reassessed at the subject's outpatient postpartum visits by study staff. The subjects will complete a measure of perceived physical disability at the outpatient postpartum visit.

**DATA COLLECTION.** Our research team members will collect the following data points from the patient's inpatient medical record: pain scale scores, medication requests/prescriptions (including name, type, and amount), time to first bowel movement, subjective incision site complaints, and time to OOB. Participants will complete a survey before discharge which will solicit additional information about the postpartum recovery experience with or without TENS therapy. (Survey is submitted with this protocol as Appendix A.) Participants will complete a survey at the 6-week postpartum visit on perceived difficulties because of health (The survey, WHODAS 2.0, is submitted with the protocol as Appendix B).

**DURATION OF STUDY.** Study duration will be no more than 12 weeks. This will include up to 6 weeks prior to delivery for study approach and consent, delivery hospitalization, and 6 weeks postpartum for pain assessments at postpartum visits. There will be no long-term follow up.

**PRIMARY and SECONDARY ENDPOINTS.** Primary endpoint of this pilot study is a total of 10 normal patients undergoing cesarean, and 10 patients with history of opioid addiction. Intervention will be performed in 5 patients in each group. Safety data will be reviewed following the first 10 patients to evaluate for worsening patient scores relative to controls.

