##### **▪ Timing and Frequency**

Survey will be performed at hospital discharge, as well as at 6 weeks postpartum.

Version Number: 5

Protocol Number: Pro2018001008

PI Name: [name]

Protocol Title: TENS after Cesarean Delivery

7

RESERVED FOR IRB STAMP

DO NOT MODIFY THIS SPACE

IRB ID: Pro2018001008

IRB Form Version: 01/2018

7/19/2022

Approval Date:

7/18/2023

Expiration Date:

7/18/2023

▪ **Location**

Surveys will be supplied to patient at bedside at discharge, and in the outpatient office during routine postpartum visit. However, if patients do not present for their routine 6 week postpartum visit, the final survey will be mailed to their last address of record, with a self-addressed stamped envelope to facilitate completion of study activities.

[figure not shown]
▪ **Procedures for Audio and Visual Recording**

N/A

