### **B. Type of Data Evaluated**

Median daily pain score, and survey results.

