### **C. Collection of Safety Information**

Direct access into the EMR at discharge, conduct of survey with the patient.

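### Staff who know the arm may administer the discharge and 6-week pain surveys, and the mode is inconsistent, so these secondary responses may lean towards TENS; self-completion before device collection is a cheap remedy

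*Protocol*

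**What the plan says.** On the discharge survey, the protocol uses two kinds of wording.

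- Staff run it. Section 1.3 states: "On the day of discharge, study staff will collect the device, and conduct a short survey about pain scores". Section 6.3.C, on collecting safety information, has: "Direct access into the EMR at discharge, conduct of survey with the patient".
- The woman fills it in. Section 1.3, under data collection, states: "Participants will complete a survey before discharge which will solicit additional information about the postpartum recovery experience with or without TENS therapy". Section 1.9 has staff provide the survey, and describes it as handed over at the bedside and in the outpatient office.

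At 6 weeks, section 1.3 has study staff reassess pain at the outpatient visit, whereas section 1.9 says that "if patients do not present for their routine 6 week postpartum visit, the final survey will be mailed".

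On contact and comparator, section 1.3 has study staff review the device with the woman again after delivery, supply it, and give her a log for time on and off; in addition, "a member of the study staff will check on the device daily to ensure proper maintenance". The design is add-on to usual care: "The intervention group will receive usual care plus TENS therapy beginning 8 hours after C-section and continuing to discharge".

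On use of the survey, section 1.6.B makes the discharge and 6-week pain surveys secondary measures. Section 6.3.B lists as the data evaluated for safety: "Median daily pain score, and survey results".

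**The concern.** In an open comparison with usual care, a self-reported score can be affected by who asks, how, and when. Here the team that teaches, supplies, checks and retrieves the device may also administer the pain survey, at about the time the device is handed back. A control woman has no device and so none of that contact; no matching visit is described for her. If women soften their pain reports to the team that gave them the device, the survey difference will include an administrator effect that the analysis cannot separate from an effect of TENS.

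Two uses are exposed. The surveys are secondary measures in a pilot meant to inform larger trials (section 1.5). Survey results also feed the safety review, whose purpose in 6.3.A includes checking that the device does not increase pain; a shift towards TENS there would work against detecting a problem.

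**Working it through.** The plan has no figure to reproduce: section 6.1.B says that no power analysis was done, and no effect size, SD or significance level is stated. The check is therefore a reading of the text, followed by an illustration of scale.

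**1. Do the staff know the arm?** Yes, by construction. Only a TENS woman has a device to collect. Neither document describes a sham or blinding of women, staff or survey administrators.

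**2. Is the discharge survey interviewer-led?** Not settled. Sections 1.3 (procedures) and 6.3.C have staff conduct it; sections 1.3 (data collection) and 1.9 (administration, location) have it provided to and completed by the woman. Both practices are compatible with the text, so women could be assessed differently. Section 1.3 names device collection before the survey but does not make that order a rule.

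**3. Is contact unequal?** Device re-teaching, the on/off log and the daily device check can apply only to the TENS arm. The check is by a member of the study staff and the survey is by study staff; the text does not say that they are the same person.

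**4. Is item order a problem?** Section 1.9.B lists the McGill Pain Questionnaire first, the Neuropathic Pain Scale second and the TENS acceptability questions third. The form itself (Appendix A) is not in the text available, so its layout, and whether controls receive the acceptability items, cannot be judged.

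**5. Which outcomes are reached?**
- Discharge survey and in-person 6-week pain assessment: reached. Both are secondary in protocol 1.6.B; the SAP's secondary list names only the 6-week surveys.
- Primary outcome: daily median pain score (protocol 6.1.A), or mean change in VAS pain over the inpatient stay (SAP). Sections 1.3 and 4.11 take inpatient pain scores from the medical record and flowsheets. Nothing says that study staff elicit them, so the survey-administrator effect does not reach them.
- Safety review: partly reached. Survey results are one of two data types in 6.3.B, but the test named in 6.3.G uses only the median daily pain score.

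**6. Does mode vary at 6 weeks?** Yes, by attendance (visit or mail), not by arm. That adds noise; it would add bias only if attendance differed between arms.

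**7. Scale, under assumed shifts.** Section 1.5 gives 4 cells × 5 = 20 women, so 10 per arm. Assume normal scores with SD 1, no true effect, and TENS responses shifted by d SD towards less pain. The expected difference in means is then d, all of it bias.

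Exact two-sided Mann-Whitney test at 0.05, 10 per arm, 20,000 simulated trials:

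| Assumed d | Significant, either direction | Significant, favouring TENS |
|---|---|---|
| 0 | 4.1% | 2.1% |
| 0.25 | 7.3% | 6.7% |
| 0.50 | 16.1% | 16.0% |
| 0.75 | 31.5% | 31.5% |

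A two-sample t test (18 degrees of freedom, noncentrality d × √(10/2)) shows the same pattern: d = 0.2, 0.3, 0.5 and 0.8 give 7.1%, 9.7%, 18.5% and 39.5% in either direction. At d = 0.2, 0.0086/0.0708, or about 12% of the significant results, favour control.

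Section 4.5.C gives 40 as the number required, against 20 in 4.5.A. If 40 meant 20 per arm, the Mann-Whitney chances favouring TENS would be about 2%, 11%, 32% and 61% for d = 0, 0.25, 0.50 and 0.75.

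**The case against.** The best defence is that much of the remedy is already a fair reading of the protocol. Sections 1.3 and 1.9 describe a form given to and completed by the woman, the pain instruments are already listed ahead of the acceptability items, and the mailed 6-week survey is a sensible guard against missing data that depends on attendance rather than arm. The primary outcome and the named safety test use charted scores. No document shows that a reporting bias exists, which way it runs, or how large it is.

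Most of this stands, and it limits the point. It does not answer the conflict with 1.3 (procedures) and 6.3.C, which let staff who know the arm conduct the survey; a site could follow either wording.

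A reader might infer more than the documents support:

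- That a face-to-face interview is settled. It is not; the wording is mixed.
- That the woman reports pain to the individual who looked after her device. Only the same team is implied.
- That all self-reported outcomes are affected, including the primary one. Inpatient scores, and under 4.11 satisfaction with pain control, come from flowsheets. Awareness of allocation and extra contact could still colour charted ratings, but that is a different mechanism, and changing the survey procedure would not remove it.
- That results will favour TENS, or that the safety review will miss worse pain. The direction is plausible but not shown, and the chart-based safety measure remains.

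**Conclusion.** The point holds in a limited form. The protocol is inconsistent on who administers the discharge survey, allows staff who know the arm to conduct it, and lets the 6-week mode vary with attendance. With no sham or blinding and with device contact in one arm only, responses to both surveys may be biased towards TENS. This affects secondary measures and one input to the safety review, not the chart-derived primary pain scores through this route.

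The size is unknown. The rates in the table depend on assumed shifts, normal data and 10 per arm; they show that a moderate shift would matter in a trial of this size, not that one will occur. The case for acting is that this part of the bias is avoidable at almost no cost, while patients' awareness of their allocation would remain.

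**What to change.** Reconcile sections 1.3, 1.9 and 6.3.C so that all three describe one procedure:

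- **Discharge.** In both arms the woman completes the survey herself and seals it in an envelope. In the TENS arm this happens before the device is collected. Staff hand out the form but do not ask the questions.
- **Order.** Keep the pain instruments first, as 1.9.B lists them. Put the TENS acceptability items last, for the TENS arm only. Check Appendix A against this.
- **6 weeks.** Use the same self-completed form at the visit or by mail, and record which route was used.

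The cost is a change of wording and possibly a re-ordered paper form, with no extra staff. The downside is a few more blank items than with staff administration. Matching daily visits to controls would address the unequal contact more directly, but their value is debatable and this correction does not depend on them.

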### **4.11 Chart/Record Review Selection**

Data will be collected by [name]. It will be collected at the time of discharge survey conduct on the RWJUH postpartum floor. Items collected from the patient's flowsheets will include pain ratings and subjective incisional complaints, number and type of pain medications used, patient satisfaction with pain control, time to first bowel movement, level of sedation and time to OOB. This will be directly imputed into an Excel spreadsheet on the investigator's password protected laptop provided by the Rutgers IT department, without identifiers.

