## **6.0 Research Data Protection and Reporting**

### **6.1 Data Management and Confidentiality**

- A. Primary outcome measures of daily median pain scores will be compared using nonparametric statistical methods. Survey responses will also be compared using Chi-square for proportions, and non-parametric methods for ordinal data.
- B. Power analysis is not performed as this is a pilot study.
- C. No PHI will be recorded in any datasheet. Data sheets will be maintained in a password protected file on the password protected principle investigators' laptop.
- D. Because all data will be collected at the time of subject discharge, data should be complete and clean for each individual at the time of collection.

Version Number: 5

Protocol Number: Pro2018001008

PI Name: [name]

Protocol Title: TENS after Cesarean Delivery

13

RESERVED FOR IRB STAMP

DO NOT MODIFY THIS SPACE

IRB ID: Pro2018001008

Approval Date: 7/19/2022

Expiration Date: 7/18/2023

**E.** Data will be shared through University secure email among study investigators only. Source data will be destroyed following data analysis, anticipated to be 1 year after completion of study procedures.

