TENS and Opioid Use After Cesarean Delivery

NCT03843788

Document Type: Statistical Analysis Plan

Document Date: 7/11/2024

Statistical Analysis Plan

All outcomes will be presented using descriptive statistics; normally distributed data by the mean and standard deviation (SD) and skewed distributions by the median and interquartile range (IQR).

Primary Outcome

The primary analysis will compare intervention groups (TENS vs usual care) on mean change in pain score as measured by Visual Analog Scale (VAS) over the course of the inpatient hospital stay. Measured primary outcomes were pain ratings, number and type of pain medications used, and patient satisfaction with pain control. Fixed effects repeated measures analysis of variance was used to evaluate the differences in pain scores between groups and Mann-Whitney tests were used to examine differences in medication intake. Additionally, repeated measures correlation (RMCORR) between TENS and usual care arms with an exploratory analysis of pain behavior in individuals with SUD compared to no SUD will be performed.

Secondary outcomes

Secondary outcomes will include pain surveys at 6 weeks postoperatively, time to first bowel movement, level of sedation, and time to out-of-bed (OOB).

Missing data

Mixed-effects procedure was utilized to avoid loss of data from missing values at different time points.

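### Time to first bowel movement is read from the chart at discharge and summarised by mean or median, with no rule for a woman discharged before the event

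*Protocol*

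**What the plan says.** - **Role.** Protocol 1.1.B hypothesises "benefits in other postpartum outcomes including time to bowel movement, level of sedation, and time to out of bed". The SAP lists these as secondary outcomes.
- **Source.** Protocol 1.3 (Data Collection) lists "time to first bowel movement, subjective incision site complaints, and time to OOB" among the items read from the inpatient record. On timing, 4.11 states: "It will be collected at the time of discharge survey conduct on the RWJUH postpartum floor". No later capture is described. Section 1.9.B lists four questionnaire components (McGill, Neuropathic Pain Scale, TENS acceptability, WHO-DAS 2.0), and none is described as recording bowel function.
- **Completeness.** Protocol 6.1.D: "Because all data will be collected at the time of subject discharge, data should be complete and clean for each individual".
- **Summary.** SAP, opening paragraph: "All outcomes will be presented using descriptive statistics; normally distributed data by the mean and standard deviation (SD) and skewed distributions by the median". The IQR accompanies the median. No between-arm test is named for these times.
- **Missing data.** SAP: "Mixed-effects procedure was utilized to avoid loss of data from missing values at different time points".
- **Not stated.** Neither document gives a time origin, a censoring rule, a time-to-event method, or a way to code a woman without the event at discharge.

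**The concern.** Collecting at discharge makes a pain score complete, but not an event time. If the event has not happened by discharge, all that is known is that the time exceeds the length of stay. Section 6.1.D overlooks this case. The SAP's mixed-effects sentence does not cover it either, because that sentence concerns repeated values at several time points and this is one event time per woman.

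A mean cannot include an unknown time, so an analyst following the SAP as written has to improvise. Leaving the cell blank removes the slowest women. Entering discharge time as if it were the event time understates theirs. Ranking them last keeps them. These choices give different answers, and nothing fixes the choice before the data are seen. With 10 women per arm, two or three such women in one arm matter. Section 1.5 offers the pilot as the basis for larger trials, so a distorted estimate could carry forward.

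**Working it through.** The plan gives no figure to reproduce: no event times, spread, effect size or length of stay for these outcomes. Every input below except the 10 women per arm (1.5) is an assumption.

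**Formulas.** Let event times be lognormal with median m and log-SD s, and let observation stop at discharge time D.

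- Share with the event observed: F = Φ(ln(D/m)/s).
- Median among observed women only: m·exp(s·Φ⁻¹(F/2)).

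**Illustration: s = 0.5, D = 72 h in both arms, medians 60 h (control) and 45 h (TENS)**

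| | Control | TENS |
|---|---|---|
| ln(D/m)/s | 0.365 | 0.940 |
| F | 0.642 | 0.826 |
| Unobserved, 1 − F | 36% | 17% |
| Φ⁻¹(F/2) | −0.465 | −0.219 |
| Observed-only median | 47.6 h | 40.3 h |

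The true difference is 60 − 45 = 15 h. The observed-only difference is 47.6 − 40.3 = 7.2 h (from unrounded values).

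**Sensitivity, same discharge time in both arms, medians 60 v 48 h (true difference 12 h)**

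| Log-SD | D = 72 h | D = 96 h | D = 120 h |
|---|---|---|---|
| 0.4 | 6.4 h | 9.5 h | 11.0 h |
| 0.6 | 4.9 h | 7.2 h | 8.9 h |

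**Discharge time differing by arm, log-SD 0.4 and 0.6**

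- Equal true medians of 60 h, control discharged at 96 h and TENS at 72 h: a spurious TENS benefit of 5.7 to 6.3 h.
- True difference 12 h (60 v 48), same discharge times: 11.2 to 12.1 h, so almost no shrinkage.
- True difference 12 h, control discharged at 72 h and TENS at 96 h: 0.8 to 3.7 h. At log-SD 0.6 the difference in means changes sign, from 14.4 to −2.1 h.

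**Trials of 10 per arm** (40,000 simulated per setting, 60 v 48 h, three settings: log-SD 0.4 with discharge at 96 h, and log-SD 0.6 with discharge at 96 h and at 72 h). At least one woman lacked the event in 82%, 98% and 100% of trials. The observed-only median difference fell below the full one in 62%, 67% and 69%. When women without the event were kept as later than discharge, the full median difference was recovered whenever both medians were reached. That happened in 99.6%, 95% and 62% of trials.

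**Out of bed** (medians 18 v 14 h and 24 v 18 h, log-SD 0.4 and 0.6). With discharge at 72 or 96 h, 0 to 3.4% per arm are unobserved. A 4 h median difference becomes 3.9 to 4.0 h, and a 6 h difference becomes 5.5 to 6.0 h. The largest effect is with discharge at 48 h, medians 24 v 18 h and log-SD 0.6: 12% of controls are unobserved and 6 h becomes 4.5 h.

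**The case against.** The best case for leaving the plan alone has five parts.

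- **Exclusion is not stated.** A reader might infer that the plan drops women without the event. No sentence says so, and a median that ranks them last would lose no one. This stands: the defect is a missing rule, not a stated exclusion.
- **The direction is conditional.** A reader might infer that the arm difference must shrink, or that the summary always works against TENS. That needs three things: such women are dropped, stays are similar by arm, and TENS truly helps. The documents establish none of them, and unequal stays can inflate, create or reverse a difference. This also stands, but a bias of unknown direction still needs a rule.
- **Time out of bed is a weak example.** Protocol 1.3 has the device taken off in hospital for toileting and showering, so discharge before first getting up should be rare. This stands.
- **The size rests wholly on assumptions.** This stands. A control median of 72 h with discharge at 48 h would lose about 85% of the difference, but there 79% of controls and 59% of TENS women are unobserved and a Kaplan-Meier median is not reached in either arm. Such extremes should not be quoted as the expected effect.
- **The stakes are low.** These are secondary outcomes in an unpowered pilot of 20, with no test named for them. This limits the importance of the point, but a descriptive estimate can still be biased.

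**Conclusion.** The point holds for time to first bowel movement. The outcome is a stated hypothesis, its observation ends at discharge, the Protocol assumes completeness at that moment, and the SAP's summary and missing-data sentence leave no usable value for a woman who has not had the event. A censored summary would be better and costs little.

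The documents support no estimate of the size. About 7 h in place of 15 h is an illustration that rests on lognormal times, the assumed medians and spread, a common discharge at 72 h, and omission of unobserved women. The direction is toward no difference only if TENS helps and stays are similar; otherwise it can go either way. For time out of bed, little effect is expected. The primary outcomes are not affected.

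**What to change.** In the SAP:

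1. Define both times as running from the end of surgery.
2. Censor a woman without the event at her discharge time.
3. Report Kaplan-Meier estimates by arm: the median where it is reached, otherwise the proportion with the event by fixed, pre-stated times.
4. Report the number censored and the time to discharge in each arm, so that a reader can judge whether stays differ or discharge is linked to recovery.
5. Apply the same rule to time out of bed for consistency.

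A log-rank test is optional in a pilot of this size. The completeness statement in Protocol 6.1.D should be qualified to match.

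Cost: a few lines of SAP text, plus discharge time, which is not among the abstraction items listed in Protocol 1.3 or 4.11 and must be added. If abstraction is already finished, this means going back to the charts. The median may also not be reached in an arm with many censored women, which is why item 3 includes proportions at fixed times.
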